Protocol Title: Functional connectivity as a biomarker of rTMS

Abbreviated Title: rTMS / functional connectivity

Protocol Number: 17-N-0055

Date of This Submission/Version: November 13, 2019/ Version H

Principal Investigator: [name]
Behavioral Neurology Unit
National Institute of Neurological Disorders and Stroke
[name]
[name]
[name]
[contact]
E-mail: [contact]

Human Research Protections Program Investigator and Staff Training:

For this protocol, the following “Just in time” human subjects protection training courses are required for investigators and staff:

- CITI GCP modules
- Unanticipated Problems and Reporting Requirements in Biomedical Research

Total requested accrual: 101

101 Healthy Volunteers

Project Uses Ionizing Radiation: No Yes

IND/IDE No Yes

Durable Power of Attorney No Yes

Multi-institutional Project No Yes

Data and Safety Monitoring Board No Yes

Technology Transfer Agreement No Yes

Samples are being stored No Yes

Flesch-Kincaid reading level of consent form: 8 (for HVs)

PRÉCIS

Objective: To use resting state functional connectivity (FC) as a biomarker of synaptic modulation by repetitive transcranial magnetic stimulation (rTMS) in paradigms intended to improve memory and learning. Ancillary outcomes include the effects of rTMS on the interaction between the explicit implicit memory systems.

Study population: Healthy adult volunteers

Design: The study contains two experiments. Experiment 1 is designed to establish the number of rTMS sessions required to produce a meaningful change in resting parieto-hippocampal FC in healthy subjects. Experiment 2 will replicate a prior experiment which used rTMS to enhance the explicit memory system in healthy subjects, and look for potential effects on the implicit system. This intervention will be contrasted with a negative control condition (vertex stimulation) in a between-groups design.

Outcome measures: The primary outcome measures are the change in FC produced by serially applied rTMS and improvement in explicit memory. We will explore whether enhancement of the explicit system has effects on resting state connectivity in the implicit system and whether white matter integrity predicts changes in FC in healthy subjects.

Table of Contents

List of Abbreviations	8
1. Introduction and Background	9
a. Background	9
b. Functional Connectivity as a stable biomarker	10
c. Dose finding using continual reassessment method (CRM)	11

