2. Study Objectives and hypotheses

The overall objective of this study is to determine whether functional connectivity can be used as a biomarker of rTMS synaptic modulation. The experiments outlined in this protocol will not be used to demonstrate the clinical effects of rTMS.

a. Aims

Experiment 1

Specific Aim 1: To determine the number of rTMS sessions required to produce a substantial change in FC between the parietal cortex and hippocampus in healthy subjects.

Experiment 2

Specific Aim 2: To determine whether rTMS delivered to the parietal cortex increases parietal-hippocampal FC in healthy subjects.

Specific Aim 3: To measure the effect of parietal rTMS on AMT and WPT-I, performance.

Specific Aim 4: To evaluate the relationship between fMRI connectivity and AMT and WPT-I outcomes after parietal rTMS in healthy subjects.

b. Hypotheses

i. Primary Hypotheses

Experiment 2: rTMS of the left parietal cortex will increase FC between the left parietal cortex and the hippocampus compared to rTMS of the vertex. rTMS of the left parietal cortex will significantly increase explicit memory compared to rTMS of the vertex.

ii. Secondary hypotheses:

Experiment 2: rTMS of the left parietal cortex will decrease FC between the left caudate (head) and parietal cortex compared to rTMS of the vertex. rTMS of the left parietal cortex will significantly decrease implicit memory compared to rTMS of the vertex.

3. Subjects

a. Description of study populations

We will study 50 healthy individuals (Experiment 1: 18; Experiment 2: 32). We are requesting up to 101 healthy volunteers as the accrual ceiling to account for dropouts and screening failures.

b. Inclusion criteria

Healthy individuals in Experiments 1 and 2.

- Age 18-50 (inclusive)
- English speaking and writing

c. Exclusion criteria

- Any current major neurological or psychiatric disorder such as (but not limited to) stroke, Parkinson disease, Alzheimer disease, schizophrenia or major depression
- History of seizure
- Medications acting on the central nervous system
- Ferromagnetic metal in the cranial cavity or eye, implanted neural stimulator, cochlear implant, or ocular foreign body
- Implanted cardiac pacemaker or auto-defibrillator or pump
- Non-removable body piercing
- Claustrophobia
- Inability to lie supine for 1 hour
- Pregnancy, nursing, or plans to become pregnant during the study.
- Members of the NINDS Behavioral Neurology Unit (BNU)
- For Experiment 2: Participation in Experiment 1

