To reduce the risks of hearing loss associated with rTMS, all subjects will be fitted with hearing protection.

8. Subject Safety Monitoring

For healthy subjects, a credentialed physician or nurse practitioner will be on site for all rTMS administration and immediately available. This is the standard of care in community and academic clinical and experimental rTMS centers, nationwide. Study staff will be trained in rTMS administration, rTMS safety, and the measurement of the motor evoked potential threshold and will have performed 10 measurements under supervision. Study staff will monitor individuals during participation and participants will be encouraged to tell experimenters of any discomfort. Any subject exhibiting distress or who wishes to stop the experiment for any reason will be allowed to stop. Participants may withdraw at any time. Data of those participants that have completed at least the first session of either Experiment 1-2 (i.e. both MRI scan and behavioral assessment) will be kept and analyzed. A researcher may end experimentation for the following reasons:

- 1) Abnormal response to rTMS including the occurrence of a seizure, loss of consciousness, or excessive pain or headache produced by rTMS.
- 2) Withdrawal of consent and/or decision to terminate.
- 3) Excessive frustration exhibited by participants on behavioral tasks.
- 4) Decision by legal proxy or patient guardian to terminate participation.
- 5) Subjects withdrawn due to high motor thresholds above the maximum capacity of the stimulator
- 6) Subjects withdrawn due to discomfort of TMS

9. Outcome Measures

a. Primary outcome measures

- Pre-to-post rTMS difference in FC between the left parietal cortex and the left hippocampus (Experiments 1-2) in healthy subjects (Experiments 1 and 2).
- Pre-to-post rTMS difference in AMT scores in healthy subjects (Experiment 2).

b. Secondary outcome measures

- Pre-to-post rTMS difference in WPT-I scores after rTMS in healthy subjects (Experiment 2).

c. Exploratory outcome measures

- Correlations between memory performance and white matter integrity (Experiment 2).

10. Statistical Analysis

a. Analysis of data/study outcomes

i. Experiment 1

Specific Aim 1: To determine the number of rTMS sessions required to produce a substantial change in FC between the parietal cortex and hippocampus in healthy subjects.

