The following aims will be investigated using the optimal sessions determined in Specific Aim 1.

ii. Experiment 2

Specific Aim 2 (Primary Aim 1): To determine whether rTMS delivered to the parietal cortex increases parietal-hippocampal FC in healthy subjects.

For each healthy subject, the Pearson correlation coefficients (r) between time courses of BOLD activity in the parietal and hippocampal areas will be calculated to determine the functional connectivity before and after rTMS stimulation. They will be Fisher-transformed to normalize r values. *We will call this the z scores.* The change in the z scores from pre- to post- stimulation will be assessed using the one-tailed, paired *t* test.

Specific Aim 3: To measure the effects of parietal rTMS on AMT and WPT-I.

First, the change in the AMT scores from pre- to post- stimulation will be calculated. Then, the two sample *t*-tests will be used to compare the changes in the AMT scores between the parietal and the sham groups. Additionally, we will consider using the Wilcoxon rank sum tests when the changes in the AMT scores are not normally distributed in each group.

Next, we will perform a similar analysis for WPT-I scores.

Specific Aim 4: To evaluate the relationship between fMRI connectivity and AMT and WPT-I outcomes in the parietal group in healthy subjects.

For each subject, the Pearson correlation coefficients (r) between time courses of the parietal and hippocampal regions will be calculated to determine the functional connectivity before and after rTMS stimulation. Then, the changes of the z scores (Fisher transformed r values) from pre- to post- simulation will be calculated. Similarly, the changes in AMT scores from pre- to post-simulation will be computed. The linear

regression models will be used to examine the relationship between the change in functional connectivity and the change in AMT scores.

Next, we will repeat a similar analysis using WPT-I scores.

b. Power analysis

Experiment 1: The maximum number of healthy subjects for Experiment 1 is set at 15.

Experiment 2: We propose to recruit 32 healthy participants (16 subjects in each of the parietal and control groups) to participate in Experiment 2.

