We based our sample size estimate on the behavioral results from the study we are replicating (Wang et al., 2014). In Wang et al. (2014), the effect size of the memory increases caused by PPC stimulation, compared to sham stimulation, was 0.75 (Cohen's d). This was achieved using a within-subjects design. Using this effect size, to achieve a β of 0.70 using the between subjects design described in this protocol (Experiment 2), 16 participants are required.

Sixteen subjects per group also achieves sufficient power to detect FC changes. Wang et al. indicate that the mean difference in FC from post to pre stimulation in retrosplenial region was 0.1018 and its standard deviation was 0.09296. Based on their data, we assume that the mean change will be between 0.1008 and 0.1028. We also assumed its standard deviation (SD) will be between 0.085 and 0.10. A one-tailed, paired t-test was used at a significance level of 0.05. Computations were carried out using PASS (Hinze J. [2008] PASS, NCSS, LLC, Kaysville, Utah).

The following table shows estimates of power to address Primary Aim 1 given ten subjects per treatment group.

Mean of paired difference	Estimated standard deviation of the difference	Power
0.1008	0.085	0.96440
0.1018	0.085	0.96698
0.1028	0.085	0.96940
0.1008	0.093	0.93446
0.1018	0.093	0.93833

0.1028	0.093	0.94202
0.1008	0.100	0.90159
0.1018	0.100	0.90651
0.1028	0.100	0.91125

Table 1. Estimated power for primary aim 1 (N=10 in parietal group)

A sample size of ten subjects per group achieves 93.8% power to detect a mean of paired differences of 0.1018 with an estimated standard deviation of differences of 0.093 and with a significance level of 5% using a one-sided paired t-test. Under other scenarios, the estimated powers were greater than 90%.

Assuming a 50% dropout rate, we anticipate enrolling up to 101 healthy subjects (33 for Experiment 1; 64 for Experiment 2).

11. Human Subjects Protection

a. Subject selection

We will recruit healthy participants through referrals from the NIH Clinical Research Volunteer program or through self-referrals to the protocol. We will work to ensure equitable selection.

b. Justification for exclusion of subjects

i. Justification for exclusion of children

Children will not be included. The study is predicated on the work of Wang et al. (2014) who studied participants over the age of 18. Therefore, in order to replicate this result, we will recruit a sample of the same age.

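### Experiment 2 has two primary hypotheses, FC and AMT, and no rule joining them; if each is tested at 0.05 and either may be claimed, the chance of a false primary claim is about 7–10%, not 5%.

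*Combined protocol and SAP*

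**What the plan says.** Three places make both endpoints primary. The précis says "The primary outcome measures are the change in FC produced by serially applied rTMS and improvement in explicit memory". Section 2.b.i gives two primary hypotheses for Experiment 2: "rTMS of the left parietal cortex will increase FC between the left parietal cortex and the hippocampus compared to rTMS of the vertex" and "rTMS of the left parietal cortex will significantly increase explicit memory compared to rTMS of the vertex". Section 9.a lists the pre-to-post differences in FC and in AMT as primary outcome measures.

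Section 10.a.ii then gives each its own analysis. For FC (Specific Aim 2, also labelled Primary Aim 1): "The change in the z scores from pre- to post- stimulation will be assessed using the one-tailed, paired" t test. For AMT (Specific Aim 3), two-sample t "tests will be used to compare the changes in the AMT scores between the parietal and the sham groups". The FC test is described as one-tailed; the AMT test carries neither a level nor a sidedness.

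The one significance level is in section 10.b and concerns FC: "A one-tailed, paired t-test was used at a significance level of 0.05". Sixteen per group is justified from the memory effect (Cohen's d of 0.75, with what is written as a β of 0.70, read here as 70% power). No section orders the hypotheses, divides alpha or says that both must succeed. No Primary Aim 2 follows Primary Aim 1.

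**The concern.** With two primary hypotheses, two separate tests and no joining rule, the plan does not say what result counts as a positive primary finding. If either may be claimed at 0.05, the familywise error of the primary claim exceeds 5%. If both are needed, the error is controlled, but the power of the study is the joint power, which section 10.b does not report.

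Experiment 2 is presented as a replication. A memory gain without an FC change, and an FC change without a memory gain, would be different conclusions, and the rule for claiming either should be fixed before the data are seen.

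**Working it through.** **Inputs.** From section 10.b: one-sided 0.05 for FC; mean FC change 0.1018 with SD 0.093; AMT d = 0.75. From sections 10.a.ii and 10.b: 16 per group, paired t test for FC, two-sample t test for AMT. Assumed: 0.05 for AMT, tried one- and two-sided, and the correlation between the two test statistics, for which the documents give no figure.

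**1. The plan's own figures.** One-sided paired t test, noncentral t, N = 10, noncentrality (0.1018/0.093)·√10 = 3.46: power 0.93833, as in Table 1. All nine cells of the table reproduce. Table 1 is for N = 10; at the planned N = 16 the stated case gives 99.4%.

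For AMT at 16 per group, noncentrality 0.75·√(16/2) = 2.12:
- one-sided 0.05: power 66.6%, and 18 per group for 70%;
- two-sided 0.05: power 53.7%, and 23 per group for 70%.

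Neither gives exactly 70% at 16, but one-sided 0.05 fits best.

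**2. Chance of at least one false primary claim, both nulls true, either result claimable.**
- Both one-sided 0.05, independent: 1 − 0.95² = 9.75%.
- Same, bivariate normal with correlation 0.3 / 0.5 / 0.7 between the statistics: 9.3% / 8.8% / 8.0%.
- AMT two-sided 0.05, counting only false claims of benefit, independent: 1 − 0.95 × 0.975 = 7.4% (6.8% at correlation 0.5).

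A simulation of the planned tests (200,000 runs, 16 per group) with subject-level correlation 0.3 / 0.5 / 0.7 / 0.9 gives 9.4% / 9.2% / 8.8% / 8.3% with AMT one-sided. The vertex group adds independent noise to the AMT contrast, so a subject-level correlation of 0.5 becomes about 0.35 between the statistics.

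**3. If both were required.** Under independence, joint power is 0.666 × 0.994 = 66% with the planned paired FC test. With a between-group FC test (d = 0.1018/0.093 = 1.095, no change in the vertex group assumed, power 91.6%), it is 0.666 × 0.916 = 61%.

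**4. Power under Holm, 16 per group, independence.** An endpoint is claimed if its p ≤ 0.025, or if its p ≤ 0.05 and the other's p ≤ 0.025. One-sided AMT power is 53.7% at 0.025 and 66.6% at 0.05.
- Paired FC test (98.3% at 0.025, 99.4% at 0.05). AMT: 0.537 + (0.666 − 0.537) × 0.983 = 66%. FC: 0.983 + (0.994 − 0.983) × 0.537 = 98.9%.
- Between-group FC test (85.0% at 0.025 by the same noncentral t calculation, 91.6% at 0.05). AMT: 0.537 + 0.129 × 0.850 = 65%. FC: 0.850 + (0.916 − 0.850) × 0.537 = 88.5%.

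**5. A weaker FC effect.** The figures 0.1018 and 0.093 are given for the retrosplenial region, whereas the primary outcome is parietal–hippocampal FC. Assume for illustration a mean change of 0.05 with the same SD: paired FC power at N = 16 is 66%. An FC-first gate would leave AMT 0.66 × 0.666 = 44%. Under Holm, AMT power cannot fall below its power at 0.025, 53.7%.

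**The case against.** The strongest reply is that this is a mechanistic study in healthy volunteers. Section 2 disclaims any demonstration of clinical effects, FC and memory are separate aims with separate hypotheses, and no study-level success criterion is defined. Whether two such questions form one error family is partly a matter of judgement. FC change alone would answer the stated objective of FC as a biomarker, and Aim 4 already examines the link between FC change and memory change. This limits the weight of the point. It does not remove it, because both hypotheses are called primary and nothing says how they may be claimed.

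A reader might infer that the error is close to double 5%. That needs AMT at one-sided 0.05 and little correlation. The documents give AMT no level or sidedness, and a two-sided test is a fair reading because only FC is called one-tailed.

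A reader might also infer that the plan treats either result alone as success. That comes from silence; the plan neither says it nor excludes it.

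Finally, the label Primary Aim 1 might suggest testing FC first and AMT only if FC succeeds. The label is tied to no gate, and section 10.b bases the sample size on the memory effect. Such a gate would demote the endpoint that sized the experiment, at a cost that depends heavily on the FC effect.

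**Conclusion.** The point holds as a gap in the plan: two primary hypotheses, separate tests, no joining rule. If each is tested at 0.05 and either may be claimed, the familywise error is about 7–10%. The top of that range, 9.75%, assumes two independent one-sided tests; the lower figure, 7.4%, assumes a two-sided AMT test and counts only false claims of benefit. The one-sided reading of AMT is supported, but not settled, by the choice of 16 per group.

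These figures concern multiplicity only. The planned FC test is pre-to-post, whereas the FC hypothesis is parietal versus vertex, so a nonspecific FC change could pass that test. Its 5% therefore does not apply to the hypothesis as stated. The change should be made, but the point does not invalidate the design.

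**What to change.** Add to section 10:

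> The two primary hypotheses of Experiment 2 (FC and AMT) are tested with the Holm procedure at an overall one-sided level of 0.05. The smaller p-value is compared with 0.025; if it is significant, the other is compared with 0.05. Both p-values are one-sided and come from comparisons of pre-to-post change between the parietal and vertex groups.

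This needs no testing order and no extra participants, and holds familywise error at 5% whatever the correlation. The last sentence is essential: it states the sidedness of AMT and makes the FC p-value answer the stated hypothesis.

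**Cost**, assuming independence and the plan's inputs at 16 per group: AMT power goes from 66.6% to about 66% and FC from 99.4% to about 98.9% if the FC test stays paired. With the between-group FC test in the wording above, AMT is about 65% and FC goes from 91.6% to about 88.5%; moving from the paired to the between-group FC test itself accounts for the drop from 99.4% to 91.6%. If FC has little effect, AMT power falls towards 54%.

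If the sponsor instead intends that both must succeed, section 10 should say so and report the joint power of 61–66%.

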3. *is for a use of substantial importance in diagnosing, curing, mitigating, or treating disease, or otherwise preventing impairment of human health and presents a potential for serious risk to the health, safety, or welfare of a subject*

TMS, as used under this protocol is not of substantial importance in diagnosing, curing, mitigating, or treating disease, or otherwise preventing impairment of human health and does not present a potential for serious risk to the health, safety, or welfare of a subject.

4. *otherwise presents a potential for serious risk to the health, safety or welfare of a subject*

TMS and its repetitive form, rTMS have been in use for over three decades and have been cleared by the FDA for treatment of several disorders. Safety guidelines have been developed (Wassermann, 1998) and updated (Rossi, Hallett, Rossini, & Pascual-Leone, 2009) allowing its dissemination to a wide range of clinical and non-clinical settings. For example, brief, self-limited, seizures were seen in early studies, before limits were established for combinations of delivery parameters. However, this risk has been reduced to the order of one in every 40,000 sessions, including for paradigms (theta-burst stimulation) not included in the guidelines (Lerner, Wassermann, & Tamir, 2019). In the past 20 years, the FDA has generally waived pre-IDE inquiries for TMS/rTMS studies on an NSR device basis. Hence, the CNS IRB, like most US IRBs, has accepted NSR designation for TMS/rTMS studies within these limitations.

Description of device

No device is specified in this protocol. TMS is delivered using standard, commercially available, equipment and guided with a frameless stereotaxic system similar to that used for neurosurgical procedures. TMS devices are cleared by the FDA for a range of applications including deep nerve stimulation and the treatment of psychiatric disorders.

Reports of prior investigations with device

The use of TMS/rTMS for investigational and therapeutic purposes was pioneered in NINDS laboratories, work which has resulted in over 1,000 publications. Worldwide, it is in use in hundreds of laboratories. See references for relevant safety literature.

Investigational plan

The objective of this study is to use resting state functional connectivity (FC) as a biomarker of synaptic modulation by repetitive transcranial magnetic stimulation (rTMS) in paradigms intended to improve memory and learning. Ancillary outcomes include the effects of rTMS on the interaction between the explicit implicit memory systems.

The study contains two experiments. Experiment 1 is designed to establish the number of rTMS sessions required to produce a meaningful change in resting parieto-hippocampal FC in healthy subjects. Experiment 2 will replicate a prior experiment which used rTMS to enhance the explicit memory system in healthy subjects, and look for potential effects on the implicit system. This intervention will be contrasted with a negative control condition (vertex stimulation) in a between-groups design.

a. Background

Repetitive transcranial magnetic stimulation (rTMS) has been attempted as a treatment for cognitive deficits in a variety of disorders (Bonni, Mastropasqua, Bozzali, Caltagirone, & Koch, 2013; Pachalska, Lukowicz, Kropotov, Herman-Sucharska, & Talar, 2011; Pape, et al., 2009). Two assumptions underlie nearly all such studies. The first of these is the notion that rTMS exerts its effects by increasing the excitability of local neurons. This came from classical observations on the effects of rTMS on MEP amplitude (the motor evoked potential), which increased after high frequency (Pascual-Leone, Valls-Solé, Wassermann, & Hallett, 1994) and decreased after low frequency (Chen, et al., 1997) stimulation. This phenomenon was likely mediated by changes in synapses on neurons located in the motor cortex (M1) at or near the stimulated site. Later attempts to influence other brain areas have generally assumed and relied on local effects and it is frequently observed that rTMS is only effective at modulating activity in superficially located areas within reach of the stimulating current. The other, related, assumption is that stimulation has been actually delivered effectively to the target region or network simply because the stimulating coil was placed in its vicinity. This premise often appears tautologically in post-hoc, mechanistic explanations of behavioral outcomes.

If rTMS were a drug, preclinical evidence of “target engagement” would be expected before interventional trials. For better or worse, however, the field of noninvasive brain stimulation has generally skipped this step. While jumping directly to clinical outcomes

may have saved time, reliable biomarkers could have been helpful by providing surrogate endpoints and better mechanistic understanding. The absence of biomarkers or similar surrogate endpoints has also made the dosing parameter space difficult to explore efficiently, since this would have to rely on behavioral endpoints in most cases. In this context, it is notable that, despite intensive research, the field has delivered only one widely adopted use whose several delivery parameters have never been optimized. Biomarkers of target engagement or surrogate endpoints with less variability than behavioral outcomes might have avoided some of the blind alleys.

Wang et al. (2014) have provided a paradigm, which may prove useful in solving these and other problems for noninvasive brain stimulation in the clinical domain. As a way to target the hippocampus, a deep structure beyond the reach of TMS, they used a conventional functional magnetic resonance imaging (fMRI) measurement, functional connectivity (FC), to find an individually customized, upstream cortical target, connected by a known monosynaptic pathway from the parietal cortex to the hippocampus. By individualizing the stimulation site using fMRI, Wang and colleagues eliminated the effect of inter-individual differences in anatomy, which can impact the results of a stimulation intervention (Karabanov, Chao, Paine, & Hallett, 2012). By applying rTMS repeatedly to this target, they caused an increase in memory performance and a correlated change in FC between the stimulated area and the area of interest deep in the brain. Incidentally, rTMS also caused dramatically increased connectivity in a network of sites related to visual memory and outside the stimulated pathway. Their work suggested that FC could be used as a marker of target engagement for noninvasive brain stimulation studies and, possibly, as an endpoint in clinical trials.

This protocol is an attempt to use FC as an endpoint, first in a dose finding study aimed at determining the number of rTMS sessions required to produce a meaningful degree of modulation in the pathway studied by Wang et al., then in an experiment involving a different pathway, and finally in a clinical trial in amnestic TBI patients.

This study is sponsored by the Center for Neuroscience and Regenerative Medicine (CNRM). To address the profound issues related to the diagnosis and treatment of TBI, the United States Congress, through Public Law 110–252, established the CNRM as a collaborative intramural program in May 2008. The CNRM is a collaborative intramural federal program involving the United States Department of Defense (DoD), the Uniformed Services University of Health Sciences (USUHS), and the National Institutes of Health (NIH) joining clinicians and scientists across disciplines to catalyze innovative approaches to TBI research.

b. Functional Connectivity as a stable biomarker

Functional connectivity is stable across scanning sessions within individuals (Barch, et al., 2013; Finn, et al., 2015). Data from 126 participants collected from the Human Connectome Project (Van Essen, et al., 2013) were used to demonstrate that participants' pattern of resting state functional activity can be reliably identified amongst sets of participants and across days (Finn, et al., 2015). For example, Finn and colleagues (2015) demonstrated that a machine classifier can identify whole brain patterns of resting

state functional connectivity across resting sessions with a success rate of at least 92.9% (see Figure 1). High test-retest reliability has been found in several studies (Biswal, et al., 2010; Shehzad, et al., 2009; Zuo, et al., 2010; Zuo, et al., 2010) and the temporal and spatial measures of resting-state networks are stable across years (Choe, et al., 2015). Thus, we are confident that FC is stable enough to use as a biomarker for the effects of rTMS in serial test sessions.

[figure not shown]

Figure 1. Results from Finn et al. (2015). Correct identification scores for machine classifier (y-axis) across eight different networks (x-axis) for FC patterns pulled from R1 and compared to the second session (R1; black bars) and for patterns pulled from the second session and compared to the first session (R2; gray bars). 1 = Medial Frontal, 2 = Frontoparietal, 3 = Default Mode, 4 = Subcortical-Cerebellum, 5 = Motor, 6 = Visual 1, 7 = Visual 2, 8 = Visual Association

c. Dose finding using continual reassessment method (CRM)

Wang and colleagues arbitrarily chose to deliver five sessions of rTMS. However, there are no empirical data on the duration of rTMS required to induce meaningful synaptic changes. Therefore, we will focus on the number of sessions as our rTMS parameter of interest while using the same stimulation parameters (e.g. frequency, intensity, duration) as Wang et al. (2014). We are choosing to focus on optimizing the number of sessions, rather than the other delivery parameters, because only one parameter can be explored at a time and reducing the number of sessions will have the greatest effect on the feasibility of this and future studies.

To find the minimum number of rTMS sessions required to produce a change in FC equivalent to that found by Wang et al., we will employ the continual reassessment method (CRM), a Bayesian, adaptive design, used to determine the dosing in Phase I drug trials. It is felt to be more efficient and accurate than simple dose escalation studies at estimating target drug doses (Garrett-Mayer, 2006). The parameter usually determined by this method is the minimum dosage expected to produce toxicity, or maximum tolerated dose (MTD). In this case, the MTD corresponds to the minimum number of sessions expected to produce the criterion change in FC. The logistical

function relating dose and effect and the MTD—the level where some predetermined proportion of subjects’ experience “toxicity”—is initially assumed from prior knowledge and then adjusted dynamically, based on response data from small cohorts of subjects dosed at successively higher or lower levels as the MTD is approximated. Cohorts are run iteratively until either a pre-specified number of participants is run, or another stopping rule has been reached (see statistical analysis section).

d. Examining the effect of rTMS stimulation on implicit and explicit memory systems

Learning and memory rely on two primary systems, an “implicit” system, which supports learning by practice and experience under feedback conditions and an “explicit” system, which supports the storage of conscious knowledge. Implicit memory relies on parallel cortical-basal ganglia loops, which operate under the modulatory influence of catecholaminergic projections from the midbrain. The explicit system resides in the hippocampus, amygdala, and related areas. These systems may be in some degree of competition (Ashby & Maddox, 2011; Ashby & Maddox, 2005; Packard & Knowlton, 2002; Poldrack & Packard, 2003). As noted above, Wang et al. (2014) targeted the hippocampus and used a test of the explicit memory system as a behavioral outcome.

In our second experiment, we will use rTMS to increase connectivity in pathways an explicit memory task. We will target the parieto-hippocampal pathway, as Wang et al. (2014) did. We hypothesize that FC will increase only in the targeted pathways and that there will be a parallel dissociation in the effects on implicit and explicit memory. This will confirm our overall hypothesis that pathways involved in specific cognitive processes can be targeted selectively. We will also include a negative control condition (vertex stimulation) to control for sensory and other nonspecific effects of rTMS.

e. Measuring mentation during resting-state scans.

Recent work has revealed that mentation patterns during resting state scanning correlates with functional connectivity measurements (Gregory et al., 2016). Because differences in mentation between participants are difficult to control and could potentially explain our results, we have decided to include a measure of mentation (the Amsterdam Resting-State Questionnaire) as an exploratory measure to our protocol (see Appendix F).

f. Targeting the implicit learning system

The original version of this protocol included a dorsolateral prefrontal stimulation arm, the purpose of which was to attempt to enhance connectivity in the implicit learning system via fronto-striatal pathways. However, this proved infeasible, due to subject discomfort. This protocol now concentrates on the effects of parietal stimulation on FC and implicit and explicit learning.

g. Enhancing hippocampal network FC in TBI patients

We originally planned to pilot the paradigm for explicit memory system enhancement in amnestic TBI patients. This plan has been dropped because of time and resource constraints.

2. Study Objectives and hypotheses

The overall objective of this study is to determine whether functional connectivity can be used as a biomarker of rTMS synaptic modulation. The experiments outlined in this protocol will not be used to demonstrate the clinical effects of rTMS.

a. Aims

Experiment 1

Specific Aim 1: To determine the number of rTMS sessions required to produce a substantial change in FC between the parietal cortex and hippocampus in healthy subjects.

Experiment 2

Specific Aim 2: To determine whether rTMS delivered to the parietal cortex increases parietal-hippocampal FC in healthy subjects.

Specific Aim 3: To measure the effect of parietal rTMS on AMT and WPT-I, performance.

Specific Aim 4: To evaluate the relationship between fMRI connectivity and AMT and WPT-I outcomes after parietal rTMS in healthy subjects.

b. Hypotheses

i. Primary Hypotheses

Experiment 2: rTMS of the left parietal cortex will increase FC between the left parietal cortex and the hippocampus compared to rTMS of the vertex. rTMS of the left parietal cortex will significantly increase explicit memory compared to rTMS of the vertex.

ii. Secondary hypotheses:

Experiment 2: rTMS of the left parietal cortex will decrease FC between the left caudate (head) and parietal cortex compared to rTMS of the vertex. rTMS of the left parietal cortex will significantly decrease implicit memory compared to rTMS of the vertex.

3. Subjects

a. Description of study populations

We will study 50 healthy individuals (Experiment 1: 18; Experiment 2: 32). We are requesting up to 101 healthy volunteers as the accrual ceiling to account for dropouts and screening failures.

b. Inclusion criteria

Healthy individuals in Experiments 1 and 2.

- Age 18-50 (inclusive)
- English speaking and writing

c. Exclusion criteria

- Any current major neurological or psychiatric disorder such as (but not limited to) stroke, Parkinson disease, Alzheimer disease, schizophrenia or major depression
- History of seizure
- Medications acting on the central nervous system
- Ferromagnetic metal in the cranial cavity or eye, implanted neural stimulator, cochlear implant, or ocular foreign body
- Implanted cardiac pacemaker or auto-defibrillator or pump
- Non-removable body piercing
- Claustrophobia
- Inability to lie supine for 1 hour
- Pregnancy, nursing, or plans to become pregnant during the study.
- Members of the NINDS Behavioral Neurology Unit (BNU)
- For Experiment 2: Participation in Experiment 1

Eligibility Checklist: See Appendix B.

4. Study Design and Methods

a. Study overview

This study will include 2 experiments, each using rTMS and MRI. Experiment 1 will use parietal rTMS. Experiment 2 will involve parietal and vertex rTMS. Experiments 2 will have the same learning and memory testing.

Experiment 1 will require a maximum of 8 visits (contingent on the results of Experiment 1) and a maximum time commitment of about 13 hours.

Experiment 2 will require a maximum of 8 visits (contingent on the results of Experiment 1) and a maximum time commitment of about 15 hours.

b. Recruitment

Healthy participants will be recruited from the pool of individuals self-referring to the study directly and via the NIH Clinical Research Volunteer Program. Although NIH employees will be allowed to participate, no direct solicitation of employees/staff by supervisors or co-workers will take place. All recruitment material will be IRB approved. Participants who indicate interest will be pre-screened over the phone. Pre-screening questions will include the following questions (Appendix A):

Are you between 18 and 50 years of age?

Are you in good health?

Are you taking any medications?

Are you prone to seizures, stroke, or migraines?

Are you free of a history of significant neurological or psychiatric conditions?

Are you free of any metal in your body?

Are you comfortable doing a one-hour MRI?

Are you able to visit the lab for up to 8 visits in a two-week period, and up to 7 visits in a week?

Participants will not be invited to participate in more than one Experiment for this protocol. Thus, participants in Experiment 1 will not be invited to participate in Experiment 2.

It is likely that some participants will miss some sessions. If this occurs, and the participant is still willing to participate, we will reschedule. If the subject has already received rTMS, we will wait at least 30 days to reschedule the session so that the effects of stimulation wash out. If a participant misses a session after baseline measures have been collected, baseline measurements will be performed again (e.g. MRI, behavioral assessments).

The study is requesting a waiver of consent documentation to conduct phone pre-screening on potential subjects prior signing main research consent to verify eligibility.

c. Screening

Participants who pass initial screening will be invited to participate in the study and scheduled for consent and formal screening.

